#### 20.8 Safety Analyses

Safety analyses will be based on the Safety Analysis Set. All safety analyses will be summarized separately by cohort. Adverse events and serious adverse events, laboratory test results, physical examination findings, vital signs, and echocardiogram results (including LVEF), and their changes from baseline will be summarized using descriptive statistics. Abnormal values will be flagged.

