# 5.3.2 Secondary objective:

- To determine the safety and tolerability of lenvatinib.
- To estimate the early tumor shrinkage rate and the deepness of response of lenvatinib in each cohort of patients.
- To estimate progression-free survival in both cohorts of patients.

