#### 6. Randomization process

Not applicable, no randomization is done in this study; all patients will receive the same study treatment independently of the cohort of the study.

[figure not shown]

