#### 9. Number of expected subjects

It is expected to include 110 patients in the study.

The study will enroll 55 patients in each cohort. Patients who meet study eligibility criteria will be stratified in cohort A or cohort B in function of primary tumor origin.

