#### 11.5 Selection and Timing of Dose for Each Subject

Study drug capsules are to be taken orally once a day at approximately the same time in the morning without regard to food intake for 28 days from Cycle 1 onward. The starting dose will be 24 mg per day. If a subject misses a dose, it may be taken within the 12 hours following the usual time of the morning dose. If more than 12 hours have elapsed from the time of the usual daily dose, study drug should be taken the next day at the usual time in the morning. In the event a subject vomits after study drug administration, the subject should not take another dose until the next scheduled dose.

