## 20.10 Adverse events

Adverse events will be graded using CTCAE v4.3. Investigators will collect all adverse event CTCAE grades (for both increasing and decreasing severity). Adverse events will be classified into standardized medical terminology from the verbatim description (investigator term) using the Medical Dictionary for Regulatory Activities (MedDRA). Adverse events will be presented by preferred term (PT) nested within system organ class (SOC). Verbatim descriptions and MedDRA SOC and PT for all adverse events will be contained in the data listings of the clinical study report for this protocol.

An overview table, including the incidence of and the number of subjects with TEAEs, SAEs, deaths, and those TEAEs that led to study drug discontinuation, dose modification, or dose interruption will be provided. The incidence of TEAEs will be summarized by SOC, PT, CTCAE grade, and relatedness to study drug. All summaries will be performed by cohort. Although a MedDRA term may be reported more than once for a subject, that subject will be counted only one time in the incidence count for that MedDRA term with the highest CTCAE grade (in the summary by CTCAE grade) or with the closest relationship to study treatment (in the summary by relatedness to study treatment). TEAEs will be defined as adverse events that emerge during treatment, having been absent pretreatment (at baseline) or those that:

- Reemerge during treatment, having been present at baseline but stopped prior to treatment, or
- Worsen in severity during treatment relative to the pretreatment state, when the adverse event is continuous.

Separate summary tables will be provided for: all TEAEs, treatment-emergent SAEs, TEAEs reported as treatment-related, treatment-emergent SAEs reported as treatment-related, and TEAEs leading to treatment discontinuation.

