#### 20.14 Echocardiograms

Echocardiograms (including LVEFs) will be assessed. Summary statistics (mean plus/minus standard deviation, median, and range) for echocardiograms and their changes from baseline will be calculated and summarized for each treatment arm.

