	Lenvatinib will be provided as 4-size hydroxypropyl methylcellulose (HPMC) capsules in 2 strengths differentiated by color: 4-mg capsule (yellowish-red cap and body) and 10-mg capsule (yellowish-red cap with yellow body). Dosing schedule of 24 mg once a day (two 10-mg capsules + one 4-mg capsule) has been selected for continued lenvatinib	
	development.	
Trial phase	II	
Objectives	Primary objective To assess the efficacy of lenvatinib on tumor objective response rate in two independent cohorts of patients with advanced neuroendocrine tumors: patients with advanced/metastatic G1/G2 pancreatic neuroendocrine tumors after progression to a previous targeted agent (cohort A), and patients with advanced/metastatic G1/G2 neuroendocrine tumors of gastrointestinal tract after failure to somatostatin analogues therapy (cohort B). Secondary objectives To determine the safety and tolerability of lenvatinib. To estimate the early tumor shrinkage rate and the deepness of response of lenvatinib in each cohort of patients. To estimate progression-free survival in both cohorts of patients. Exploratory objectives To evaluate biochemical response (changes in CgA and NSE levels) and its association with response rate and progression-free survival. To assess whether baseline tumor and blood biomarkers may be predictive of response to lenvatinib. To explore additional hypotheses related to biomarkers and relationship to lenvatinib, neuroendocrine tumors, other	

Page 5 of 16 Date: June 04, 2020

TALENT Statistical Analysis Plan	Version 2.0 Date: June 04, 2020		
	endocrine disorders and/or cancer which may arise from internal or external research activities.		
Design	Prospective, international, multi-center, open label, stratified, exploratory phase II study evaluating the efficacy and safety of lenvatinib.		
Primary endpoint	The primary endpoint of the study is overall response rate (ORR) by RECIST v 1.1 upon central radiologic assessment.		
Study population and total number of subjects	Patients with advanced/metastatic, histologically confirmed, grade 1/2 (G1/G2) of 2010 WHO classification neuroendocrine tumors of the pancreas after progression to a previous targeted agent (cohort A) or gastrointestinal tract after progression to somatostatin analogues (cohort B). Number of patients: 110 patients in total (55 per each cohort).		
Approximate duration of subject participation	24 months		

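### Safety is planned by cohort only; a combined column for all patients on the same drug and starting dose should be added beside the cohort columns

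*Protocol*

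**What the plan says.** Protocol 20.8 sets the general rule: "All safety analyses will be summarized separately by cohort". SAP 6.2.1 repeats that sentence under the first secondary objective. Protocol 20.10 adds for adverse events: "All summaries will be performed by cohort". Protocol 20.9 (exposure) and 20.11 (laboratory values) name no grouping, so the rule in 20.8 governs them. Protocol 20.14 says echocardiogram results are "calculated and summarized for each treatment arm". As Protocol 5.3 calls the trial a two-arm study, this most likely also means by cohort. No section of either document plans a safety summary of both cohorts together.

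The objectives are worded differently. The safety objective reads "To determine the safety and tolerability of lenvatinib", with no mention of cohort. The next one in the same list reads "To estimate the early tumor shrinkage rate and the deepness of response of lenvatinib in each cohort of patients", and the progression-free survival objective also refers to both cohorts.

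Treatment does not differ by cohort. Protocol 6 says "all patients will receive the same study treatment independently of the cohort of the study", and Protocol 11.5 says "The starting dose will be 24 mg per day". One dose-modification table (Protocol 11.7) and one set of adverse-event collection rules (Protocol 14) apply to everyone.

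On numbers, Protocol 9 says "It is expected to include 110 patients in the study", with 55 in each cohort.

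**The concern.** The objective asks about the drug, while the planned tables answer for each cohort. The cohort size was fixed by the response-rate hypothesis in Protocol 20.6, not by a safety consideration, and no reason is given for omitting a combined summary. Each planned safety estimate therefore uses half of the patients exposed to the same regimen.

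The stake is precision. It matters most for uncommon toxicities, where one patient in each cohort is harder to interpret than two patients in a combined column. It also matters for summaries that are not counts. Median exposure or median laboratory change over all patients cannot be worked out from two cohort medians, so what is not planned there is not recoverable from the printed tables.

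**Working it through.** **Inputs.** 55 per cohort and 110 in total (Protocol 9 and 20.6). These are ceilings, because the Safety Analysis Set (Protocol 20.2, SAP 5) also requires a dose of study drug and a post-baseline safety evaluation. The documents give no adverse-event rates for this population, so the rates below are assumptions.

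**Where the 55 comes from.** Protocol 20.6 uses a single-stage design with an unacceptable response rate of 10%, an expected rate of 25%, a 5% level and 90% power. With an exact binomial test that declares success at 10 or more responses in 55:

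- P(X ≥ 10 | n = 55, p = 0.10) = 0.0444
- P(X ≥ 10 | n = 55, p = 0.25) = 0.9112

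55 is the smallest number that meets a one-sided 5% level with 90% power, so the plan's figure reproduces. It is purely an efficacy calculation.

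**Interval width at an observed 20%** (exact Clopper-Pearson, two-sided 95%). This rate gives the same proportion at both sizes.

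| Patients | Events | 95% interval | Width |
|---|---|---|---|
| 55 | 11 | 10.4% to 33.0% | 22.5 points |
| 110 | 22 | 13.0% to 28.7% | 15.7 points |

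The ratio is 22.5 / 15.7 = 1.43, close to the √2 = 1.41 expected from doubling the sample.

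**No events seen.** The upper limit is 1 − 0.025^(1/n).

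- n = 55: 1 − 0.025^(1/55) = 6.5%
- n = 110: 1 − 0.025^(1/110) = 3.3%

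**Chance of a repeated event at an assumed 2% true rate.** P(X ≥ 2) = 1 − (1 − p)^n − n·p·(1 − p)^(n−1).

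- One given cohort: 1 − 0.98^55 − 55 × 0.02 × 0.98^54 = 1 − 0.3292 − 0.3695 = 0.301
- At least one of the two cohorts: 1 − (1 − 0.301)² = 0.51
- Combined: 1 − 0.98^110 − 110 × 0.02 × 0.98^109 = 1 − 0.1084 − 0.2433 = 0.648

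Because the plan reports both cohorts, the fair comparison is 51% with 65%. The difference of about 14 points is the chance of exactly one case in each cohort: 0.3695² = 0.137.

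**Range of assumed rates.**

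| True rate | Given cohort | At least one cohort | Combined |
|---|---|---|---|
| 1% | 10.5% | 19.9% | 30.1% |
| 2% | 30.1% | 51.2% | 64.8% |
| 3% | 49.4% | 74.4% | 84.6% |

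The gain from combining is 10 to 14 points across this range.

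**The case against.** The strongest case against is that this is a matter of table layout. The cohorts are disjoint, and under Protocol 20.10 a subject counts once per MedDRA term, so cohort counts add exactly: 1/55 and 1/55 make 2/110. Protocol 20.10 also puts every adverse event in the study report listings. By-cohort reporting suits the design. Cohort A has had a previous targeted agent and may have had one line of chemotherapy, both of which exclude a patient from cohort B, and tolerability could differ for that reason. If the rates do differ, the combined figure describes a mix fixed by the enrolment quotas. Confidence intervals for adverse-event rates are optional under Protocol 20.7, so the interval comparison concerns output that the plan does not promise.

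Much of this stands. It rules out three stronger readings that a reader might infer:

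- **That toxicity on the full sample can never be known.** Crude incidences are recoverable by addition. What is absent is a planned combined summary.
- **That serious events would be missed.** Serious events are reported within 24 hours whatever their cause (Protocol 14.5.1), and suspected unexpected serious reactions go to the authorities (Protocol 14.7). Neither route depends on these tables, and no stopping or success rule uses them.
- **That the chance of seeing a repeated event rises from 30% to 65%.** The 30% applies to one cohort named in advance. With both cohorts reported it is 51%.

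The objection does not remove the point. A combined column leaves the cohort columns intact, so any difference in tolerability stays visible. Addition also does not work for medians.

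**Conclusion.** The point holds as a minor reporting gap. The planned safety summaries do not include the all-patient estimate that the wording of the safety objective calls for, and each planned estimate rests on at most 55 of at most 110 patients. Combining narrows exact 95% intervals by a factor of about 1.4 and halves the zero-event upper limit from 6.5% to 3.3%. At an assumed 2% rate it raises the chance of seeing a repeated event from 51% to 65%.

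The gain in precision assumes that the cohorts have similar rates, which the documents neither state nor rule out. The numbers also assume full enrolment and that every patient enters the Safety Analysis Set.

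The documents do not support treating by-cohort reporting as an error, or replacing the cohort figures with the combined one, because the cohorts differ in tumour origin and prior therapy. The primary response-rate analysis and its sample size are unaffected.

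**What to change.** Amend Protocol 20.8, Protocol 20.10 and SAP 6.2.1 to read: *Safety will be summarised by cohort and for both cohorts combined, on the Safety Analysis Set.* State that this covers exposure and laboratory summaries as well as adverse events, and align the grouping term in Protocol 20.14 with the other sections. Head the combined column with the name of the analysis set, since that set may be smaller than the number dosed.

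Give exact 95% intervals for the incidence of key adverse events, as Protocol 20.7 already permits. Read the combined column beside the cohort columns, and comment where the cohorts differ.

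The cost is one column in tables already planned. No new data are needed and no cohort information is lost.

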#### 20.9 Extent of exposure

The number of cycles/days on treatment, quantity of study drug administered, and the number of subjects requiring dose reductions, treatment interruption, and treatment discontinuation due to adverse events will be summarized.

## 20.10 Adverse events

Adverse events will be graded using CTCAE v4.3. Investigators will collect all adverse event CTCAE grades (for both increasing and decreasing severity). Adverse events will be classified into standardized medical terminology from the verbatim description (investigator term) using the Medical Dictionary for Regulatory Activities (MedDRA). Adverse events will be presented by preferred term (PT) nested within system organ class (SOC). Verbatim descriptions and MedDRA SOC and PT for all adverse events will be contained in the data listings of the clinical study report for this protocol.

An overview table, including the incidence of and the number of subjects with TEAEs, SAEs, deaths, and those TEAEs that led to study drug discontinuation, dose modification, or dose interruption will be provided. The incidence of TEAEs will be summarized by SOC, PT, CTCAE grade, and relatedness to study drug. All summaries will be performed by cohort. Although a MedDRA term may be reported more than once for a subject, that subject will be counted only one time in the incidence count for that MedDRA term with the highest CTCAE grade (in the summary by CTCAE grade) or with the closest relationship to study treatment (in the summary by relatedness to study treatment). TEAEs will be defined as adverse events that emerge during treatment, having been absent pretreatment (at baseline) or those that:

- Reemerge during treatment, having been present at baseline but stopped prior to treatment, or
- Worsen in severity during treatment relative to the pretreatment state, when the adverse event is continuous.

Separate summary tables will be provided for: all TEAEs, treatment-emergent SAEs, TEAEs reported as treatment-related, treatment-emergent SAEs reported as treatment-related, and TEAEs leading to treatment discontinuation.

#### 20.11 Laboratory values

Clinical laboratory values will be evaluated for each laboratory parameter by subject. Abnormal laboratory values will be identified as those outside (above or below) the normal range. Reference (normal) ranges for laboratory parameters will be included in the clinical study report for this protocol. Descriptive summary statistics for laboratory parameters and their changes from baseline will be calculated. Laboratory parameters that are graded in CTCAE v4.03 will be summarized by CTCAE grade.

#### 20.12 Vital signs

Vital sign values will be evaluated on an individual basis by subject. Abnormal vital sign values will be identified as those outside (above or below) the reference range. Reference ranges for vital sign parameters will be included in the clinical study report for this protocol. Descriptive summary statistics for vital sign parameters and their changes from baseline will be calculated.

#### 20.13 ECG results

ECG results will be evaluated on an individual basis by subject. Abnormal readings will be identified as those outside the reference range. ECG findings will be summarized.

An abnormal ECG result, if not otherwise considered part of a clinical symptom that is being reported as an AE, should be considered an AE if either there is worsening by  $\geq$  2 CTCAE v4.03 grade levels from baseline or a QTc increase of  $\geq$ 60 msec from baseline. Any ECG abnormality that the investigator considers to be an adverse event should be reported as such.

#### 20.14 Echocardiograms

Echocardiograms (including LVEFs) will be assessed. Summary statistics (mean plus/minus standard deviation, median, and range) for echocardiograms and their changes from baseline will be calculated and summarized for each treatment arm.

## Appendix I Response Evaluation Criteria in Solid Tumors (RECIST) 1.1

Tumors (RECIST 1.1) based on the 2009 article by Eisenhauer et al entitled, New Response Evaluation Criteria in Solid Tumors (RECIST 1.1) based on the 2009 article by Eisenhauer et al entitled, New Response Evaluation Criteria in Solid Tumors: revised RECIST guideline (version 1.1). The sole modification to RECIST 1.1 to be implemented in this trial is that chest x-rays may not be used to follow disease; only CT scans may be used to follow chest disease. As required by RECIST 1.1, the protocol states that the minimum duration of stable disease is 7 weeks following the date of first dose of study drug. The Eisenhauer article, published in the European Journal of Cancer, is available online at: http://linkinghub.elsevier.com/retrieve/pii/S0959804908008733.

# **Appendix II: Eastern Cooperative Oncology Group Performance Status**

Scale	ECOG Status  Fully active, able to carry on all pre-disease performance without restriction	
0		
1	Restricted in physically strenuous activity but ambulatory and able to carry out work of a light or sedentary nature (eg, light house work, office work).	
2	Ambulatory and capable of all self-care, but unable to carry out any work activities. Up and about more than 50% of waking hours.	
3	Capable of only limited self-care, confined to bed or chair more than 50% of waking hours.	
4	Completely disabled. Cannot carry on any self-care. Totally confined to bed or chair.	
5	Dead.	

ECOG = Eastern Cooperative Oncology Group.

Adapted from Oken MM et al. Am J Clin Oncol. 1982;5:649-55.

## **Appendix III Cockcroft and Gault Formula**

Male 
$$\frac{(140\text{-age}) \text{ x weight (kg)}}{\text{Serum creatinine (mg/dL) x 72}} = XX \text{ mL/min}$$
Female 
$$\frac{(140\text{-age}) \text{ x weight (kg) x 0.85}}{\text{Serum creatinine (mg/dL) x 72}} = XX \text{ mL/min}$$

Adapted from Cockcroft DW et al. Nephron. 1976;16(1):31-41.

For serum creatinine measured in µmol/L:

Male 
$$\frac{(140\text{-age}) \text{ x weight (kg) x 1.23}}{\text{Creatinine (µmol/L)}} = XX \text{ mL/min}$$
Female 
$$\frac{(140\text{-age}) \text{ x weight (kg) x 1.23 x 0.85}}{\text{Creatinine (µmol/L)}} = XX \text{ mL/min}$$

# Appendix IV: Common Terminology Criteria for Adverse Events (CTCAE v4.03)

The National Cancer Institute's Common Terminology Criteria for Adverse Events (CTCAE v4.03 published 14 June 2010) provides descriptive terminology to be used for adverse event reporting in clinical trials. A brief definition is provided to clarify the meaning of each AE term. To increase the accuracy of AE reporting, all adverse event terms in CTCAE version 4.03 have been correlated with single-concept, Medical Dictionary for Regulatory Activities (MedDRA®) terms.

CTCAE v4.03 grading refers to the severity of the AE. CTCAE grades 1 through 5, with unique clinical descriptions of severity for each AE, are based on this general guideline:

Grade	CTCAE Status	
1	Mild: asymptomatic or mild symptoms; clinical or diagnostic observations only; intervention not indicated.	
2	Moderate: minimal, local, or noninvasive intervention indicated; limiting age- appropriate instrumental activities of daily living (ADL). a	
3	Severe or medically significant but not immediately life-threatening: hospitalizatio or prolongation of hospitalization indicated; disabling, limiting self-care ADL. b	
4	Life-threatening consequences: urgent intervention indicated.	
5	Death related to adverse event.	

CTCAE = Common Terminology Criteria for Adverse Events.

a: Instrumental ADL refers to preparing meals, shopping for groceries or clothes, using the telephone, managing money, etc.

b: Self-care ADL refers to bathing, dressing and undressing, feeding self, using the toilet, taking medications, and not bedridden. Adapted from the Cancer Therapy Evaluation Program, NCI. CTCAE v4.0. Available from http://ctep.cancer.gov/protocolDevelopment/electronic applications/docs/ctcaev4.pdf.

#### **Appendix V Drug-Drug Interactions**

Preliminary preclinical studies identify CYP3A4 as an important enzyme responsible for human hepatic metabolism of E7080. Caution should be exercised when administering drugs metabolized by CYP3A4 or drugs that are inductors or inhibitors of CYP3A4 (including herbal supplements, or large amounts of grapefruit juice), as administration of such drugs could affect the metabolism of E7080 (see table below).

Table 6 Drugs That Affect the Activity of CYP3A4

Class of Drug	Drug Name	
Drugs that inhibit CYP3A4 strongly	azole antifungal agent	itraconazole ketoconazole
	macrolide antibiotic agent	clarithromycin
	ketolide antibiotic agent	telithromycin
	anti-HIV agent	atazanavir indinavir saquinavir nelfinavir ritonavir
	antidepressant agent	nefazodone
Drugs that induce CYP3A4 strongly	antitubercular agent	rifampicin
	antiepileptic agent	carbamazepin

Abbreviations: CYP3A4, cytochrome P450 3A4; HIV, human immunodeficiency virus.

This list of clinically relevant agents is from: http://medicine.iupui.edu/clinpharm/DDIs/ClinicalTable.asp. Accessed 15.Jun.2009.

Please refer to this website for the most up-to-date listing and to the product inserts for more information. Caution should be exercised for CYP3A4 substrates with a narrow therapeutic index. A representative, but not exhaustive, list of examples includes astemizole, cisapride, cyclosporine, diergotamine, ergotamine, erythromycin, opioid analgesics (alfentanyl, codeine, fentanyl, levomethadyl acetate (LAAM), methadone), pimozide, quinidine, sirolimus, tacrolimus, and terfenadine.

Page 85 of 88 Date: April 04th, 2016

